# 4.2 Study Calendar

	Pre-treatment	Week 1	Week 5*	Week 9*	Week 13*	Week 25 & 49#
History and Physical Examination	Х	Х	Х	Х	Х	Х
Adverse Event Assessment	Х	Х	Х	Х	Х	Х
Questionnaires: DLQI, PROMIS	Х	Х	Х	Х	Х	Х
Photos	Х	Х	Х	Х	Х	Х
Ultrasound	Х		Х	Х	Х	Х
Blood Tests: CBC, CRP, ESR	Х	-	-	-	Х	Х
Serum or Urine Pregnancy Test	×	-	-	-	-	-
Skin Biopsy, Discharge Measurement	×	-	-	-	Х	Х
Radiotherapy	-	XXXXX	-	-	-	-

\*+/- 1 week

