#### Interim Analysis.

Once the first 6 patients are recruited, the study recruitment will be temporarily suspended and the patients will be followed for 3 months to monitor any toxicity issues. At the end of 3 months follow-up of the 6 patients, the results will be sent to the DSMB for further evaluation. The trial will be terminated if grade 3 or more toxicity is observed in more than 2 patients or at least one showing grade 4 level toxicity. Otherwise, upon approval from the DSMB, the second phase of recruiting will be initiated.

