# 4.3 Study Endpoints

The primary endpoint of this study is safety, defined as the absence of any treatment-related Grade ≥3 adverse events during radiotherapy or within 3 months of radiotherapy completion, scored using CTCAE version 4.0.[6] Secondary study endpoints include:

# Optional

- Quality of Life
  - Improvement in NIH Patient-Reported Outcomes Measurement Information System (PROMIS) measures, including pain interference and physical functioning at 3 months (and optionally at 6 months and 12 months) after treatment[7, 8]
    - A one point change, either positive (improvement) or negative (decline), will be considered to be clinically meaningful[9]
- Inflammation as measured by ultrasound.
  - Noninvasive imaging, such as ultrasound (US), allows for an objective assessment of subclinical disease activity.
  - Anechoic area will be measured in the dermis before and after treatment, as well as other sonographic criteria of HS [10](See Appendix for Sonographic Scoring and Diagnosis of HS)
  - As there are no validated ultrasound criteria to measure clinical improvement, reduction in anechoic areas and sonographic criteria will be calculated. It is estimated that the treatment will induce a 50% reduction in the anechoic area.
  - Anechoic areas and other sonographic criteria will be correlated with PROMIS scores and Hurley Staging.
- Evaluation of cutaneous discharge
  - Swabs will be collected from discharge and sent for fluid count, which will include evaluation of infiltrating leukocytes from the discharge.
- Immunohistochemical Evaluation of HS Tissue Biopsies
  - Tissue biopsies will be collected before and after treatment. Tissue sections will be evaluated by H&E as well as immunohistochemistry for infiltrating leukocytes and other cells, such as T cells, B cells, plasma cells, dendritic cells, macrophages, and keratin. Image J will be used to quantify cells in a standard manner for comparison before and after treatment.

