#### 5.0 STATISTICAL CONSIDERATIONS

A maximum of 20 patients will be enrolled into the study. The accrual rate is expected to be 1-2 patients per month based on the volume of patients with stage 2-3 HS treated within the Montefiore Hidradenitis Suppurativa Treatment Center. An early stopping rule for safety will be implemented as follows based on Simon's optimal two-stage design. After the first 6 patients have been enrolled, accrual will be temporarily suspended while these patients are monitored for occurrence of treatment-related grade ≥ 3 toxicity for 3 months. At the end of 3

months, results will be sent to the DSMB for further evaluation. The trial will be terminated early if more than 1 patient experiences grade  $\geq$  3 treatment related toxicity or any patient experiences grade 4 toxicity. Otherwise, upon approval from the DSMB, the second phase of recruiting will be initiated. If 1 or fewer grade  $\geq$  3 toxicities and 0 grade 4 toxicities are observed, the trial will continue until a total of 20 patients have been evaluated. At the end of the trial, the treatment will be considered safe and worthy of further study if no more than 3 patients experience grade  $\geq$  3 treatment related toxicity and none experience grade 4 treatment related toxicity.

The target Grade  $\geq$  3 toxicity rates is no more than 10%, and a toxicity rate greater than 30% is considered clinically unacceptable. The design specified above has the following operating characteristics. The probability of accepting the treatment for further study if the toxicity rate is unacceptably high (> 30%) is at most 10%. In contrast, there is an 80% probability of accepting the treatment for further study if the toxicity rate is less than 10%. In addition, if 0 out of 20 patients experience Grade 4 toxicity at the end of the study, we will be able to conclude with 95% confidence that the true Grade 4 toxicity rate is not greater than 17%.

The proportion of patients who have treatment-related toxicity will be computed, along with exact 95% confidence intervals. Since the study is a phase I trial, we will NOT do any hypothesis testing or models, The study will present the descriptive summary statistics for each outcomes. Biomarker levels measured at different time points and other continuous variables will be summarized by computing means, medians, standard deviations and ranges.

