### 10.0 RISKS/BENEFITS

- Anticipated risks (medical, social, psychological, and/or legal)
  - This protocol is considered greater than minimal risk, due to radiation exposure and the skin biopsy procedure.
  - The initial risk of radiotherapy is temporary discomfort and inconvenience during the treatment period.
  - This dose of radiotherapy may cause temporary hair loss at the treatment site for a few months.
  - The risk of acute or chronic radiation-induced dermatitis is thought to be very low with the dose of radiotherapy being employed in this study.
  - A risk of low-intermediate dose radiation is Radiation Induced Cancer (RIC) such as skin cancer (BCC, SCC, melanoma)[2]. In patients treated for benign disease with intermediate dose radiotherapy (Range 3-50 Gy, mean approximately 20Gy), normal tissue side effects are rare or minimal. RIC risk is normally very small in adults (<1%) and decreases with increasing age.

  - o Blood draw may cause discomfort, pain, and bruising.
  - Risks from skin biopsy may include temporary pain during the procedure, a small chance of infection, and the possibility that biopsy leaves a small scar.
  - A psychological risk is that the treatment will not have any clinical improvement.
  - o Breach of confidentiality is a possible risk if data is lost or stolen.
- How anticipated risks will be minimized
  - To minimize RIC risks- careful body positioning during radiotherapy and shielding of tissues outside of the intended treatment field will be

- employed in a customized fashion for each patient. In most cases, treatment with superficial forms of radiotherapy (electrons or surface brachytherapy) will be employed to minimize the volume of tissue irradiatied.
- Lab tests and skin biopsy will be performed carefully, using standard safety measures.
- o Confidentiality will be maintained as described in Section 7.1.
- Potential benefits
  - Potential benefits include disease improvement and potential remission, along with improved quality of life

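### The last mandatory adverse-event check falls on the same visit as the only mandatory post-radiotherapy biopsy (Week 13 +/- 1 week), and an early visit ends about a week before the 3-month safety window closes

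*Combined protocol and SAP*

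**What the plan says.** The Section 4.2 calendar marks "Skin Biopsy, Discharge Measurement" at pre-treatment, Week 13, and Weeks 25 and 49. It marks "Adverse Event Assessment" at every visit: pre-treatment, Weeks 1, 5, 9 and 13, and Weeks 25 and 49. Weeks 5, 9 and 13 carry an allowance of one week either way. Weeks 25 and 49 are footnoted as optional, and Section 4.3 agrees in timing the PROMIS outcome "at 3 months (and optionally at 6 months and 12 months) after treatment".

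The primary endpoint in Section 4.3 is "the absence of any treatment-related Grade ≥3 adverse events during radiotherapy or within 3 months of radiotherapy completion". For the first six patients, the Interim Analysis text in Section 4.1 says: "At the end of 3 months follow-up of the 6 patients, the results will be sent to the DSMB for further evaluation". Section 5.0 repeats the 3-month monitoring period.

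On biopsy harm, Section 10.0 says: "Risks from skin biopsy may include temporary pain during the procedure, a small chance of infection, and the possibility that biopsy leaves a small scar". The only precaution it gives is this: "Lab tests and skin biopsy will be performed carefully, using standard safety measures". Section 9.0 refers adverse-event definitions and reporting to an institutional policy that is not among the documents. Section 8.0 provides for committee review of events of grade 3 or higher.

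**The concern.** There are two gaps at the same visit.

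The first is the biopsy. Infection develops after the procedure, so an assessment made at the biopsy visit cannot see it. If the calendar is followed exactly, a patient who declines the optional visits is never asked about the Week 13 biopsy site. The reporting clauses deal with events that are already known; they do not create a contact that would find one. Section 10.0 gives the biopsy as one of its two reasons for rating the study above minimal risk.

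The second, smaller gap is the safety window. The primary endpoint runs to 3 months after the last fraction, but the allowance lets the final mandatory assessment fall before that. A patient seen early would be counted as event-free for days on which nobody was scheduled to look.

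At stake are protection of the participant after a research biopsy and completeness of the data behind the primary endpoint.

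**Working it through.** **Assessments after each biopsy (Section 4.2)**

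| Biopsy | Mandatory adverse-event assessments afterwards |
|---|---|
| Pre-treatment | 4 (Weeks 1, 5, 9, 13) |
| Week 13 | 0 |

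The next assessment after Week 13 is optional and 25 - 13 = 12 weeks later.

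**Which visit is the 3-month visit.** Subtracting the treatment week from 5, 9, 13, 25 and 49 gives 4, 8, 12, 24 and 48 weeks. Week 13 is thus the 3-month visit, and the calendar's own spacing suggests 3 months = 12 weeks = 84 days. The plan does not state this in days, so 91 days (13 weeks) is carried as an alternative.

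**Inputs.** Week w covers days 7(w - 1) + 1 to 7w, so Week 13 is days 85-91. One week early is days 78-84 and one week late is days 92-98. The allowance therefore covers days 78-98. Radiotherapy is five daily fractions in Week 1; I assume that it ends on day 5.

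**Window close.** Last fraction + 3 months: 5 + 84 = day 89, or 5 + 91 = day 96.

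**Shortfall = closing day - visit day**

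| Visit | 84 days (closes day 89) | 91 days (closes day 96) |
|---|---|---|
| Early, days 78-84 | 89 - 84 = 5 to 89 - 78 = 11 days short | 96 - 84 = 12 to 96 - 78 = 18 days short |
| On time, days 85-91 | 89 - 85 = 4 days short to 91 - 89 = 2 days past | 96 - 91 = 5 to 96 - 85 = 11 days short |
| Late, days 92-98 | 92 - 89 = 3 to 98 - 89 = 9 days past | 96 - 92 = 4 days short to 98 - 96 = 2 days past |

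An early visit on the same weekday as the last fraction is day 82, which is 82 - 5 = 77 days after radiotherapy and 84 - 77 = 7 days short. That is the source of 'about a week'. If radiotherapy ends on day 7 instead, every closing day moves 2 days later and each shortfall grows by 2 days.

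**Check of the proposed call.** The call is due at the later of biopsy + 14 days and the closing day. On the 91-day definition:
- Visit on day 78: 78 + 14 = 92, before day 96, so the call moves to day 96, which is 18 days after the biopsy.
- Visit on day 82 or later: 82 + 14 = 96, so the 14-day point is already late enough.
- Visit on day 98: 98 + 14 = day 112.

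On the 84-day definition the earliest call is day 92, already past day 89. Every permitted visit date therefore leads to an assessment at or after the close of the window.

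**The case against.** The strongest reply is that this lies beside the trial's question. The objective is the safety of radiotherapy, and only treatment-related events of Grade 3 or higher count. Section 10.0 describes the infection risk as small. All of that stands. A reader might infer that the primary conclusion or the stopping rule is unreliable; the documents do not support that, because a biopsy-site infection would seldom be both severe and attributed to radiotherapy.

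A reader might also try to attach a missed-infection rate or a confidence limit to the gap. The plan's exact intervals are for treatment-related toxicity. It estimates no biopsy-infection rate and gives no attendance figure for the optional visits, so any such number would be invented.

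Nor can one conclude that patients receive no wound advice. Consent pages are outside the reviewed text, the institutional policy is not available, and Section 7.3 makes the electronic medical record the main data source, so an infection treated at the institution may surface there. What stands is narrower: no contact or record review after the biopsy is written into the plan.

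On the window, it is fair to say that Sections 4.1 and 5.0 already require 3 months of follow-up before the interim review. With "The accrual rate is expected to be 1-2 patients per month", patients are about 30/2 = 15 to 30/1 = 30 days apart, so most of the first five will have passed 3 months when the sixth is seen. A reader should not infer that the DSMB is meant to decide on short follow-up. But elapsed time is not assessment: a patient seen on days 78-84 has no later mandatory visit at which the remaining days are examined. The interim text also does nothing for the patients enrolled after the first six.

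Finally, it would be too strong to say that the Week 13 visit as such misses the window. On the 84-day reading an on-time visit is roughly at the boundary; only on the 91-day reading is it clearly short.

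**Conclusion.** The point holds as a modest gap in participant protection and ascertainment. By the calendar, up to 20 of 20 patients have a mandatory Week 13 biopsy with no mandatory assessment after it. An early Week 13 visit ends mandatory assessment 5 to 11 days before an 84-day window closes, or 12 to 18 days before a 91-day window closes. These day counts assume that radiotherapy ends on day 5, and the choice between them depends on a definition of 3 months that the plan does not give. The biopsy part needs neither assumption.

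No number of missed events is claimed, and a different Grade 3 or higher result is unlikely. The case for acting is that the remedy is cheap, safety is the primary objective, and without a written check a report of no biopsy infections could not be told apart from not having looked in patients who skip the optional visits.

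**What to change.** Keep the Week 13 visit and its allowance of one week either way. Narrowing it would make the main safety visit harder to schedule.

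1. In Section 4.3, state 3 months in days from the last fraction, for example 91.
2. In Section 4.2, add one footnote: *For every patient, existing staff make one adverse-event telephone call and review the medical record about 2 weeks after the Week 13 biopsy and no earlier than 3 months after the last fraction.* The 2 weeks is my suggestion; the documents give no interval.
3. In Sections 4.1 and 5.0, for the first six patients, require adverse-event status through 3 months after the last fraction, from the visit or the call, in the DSMB report. Later biopsy-site findings follow as an addendum.

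The cost is at most 20 short calls and 20 record reviews, with no new visit or procedure. There are three downsides:
- The call relies on self-report.
- With 91 days, and radiotherapy ending on day 5, only visits on days 96-98 reach the end of the window, so for most patients the call closes it. With 84 days, visits on days 89-98 do.
- If the sixth patient's visit falls before 3 months, the DSMB report may wait about 2 weeks for the call. The extreme is 18 days after a day-78 visit, but that wait ends on day 96, the 3-month date itself. Measured from that date, the longest wait is for a day-95 visit: 95 + 14 - 96 = 13 days.

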# 4.3 Study Endpoints

The primary endpoint of this study is safety, defined as the absence of any treatment-related Grade ≥3 adverse events during radiotherapy or within 3 months of radiotherapy completion, scored using CTCAE version 4.0.[6] Secondary study endpoints include:

# Optional

- Quality of Life
  - Improvement in NIH Patient-Reported Outcomes Measurement Information System (PROMIS) measures, including pain interference and physical functioning at 3 months (and optionally at 6 months and 12 months) after treatment[7, 8]
    - A one point change, either positive (improvement) or negative (decline), will be considered to be clinically meaningful[9]
- Inflammation as measured by ultrasound.
  - Noninvasive imaging, such as ultrasound (US), allows for an objective assessment of subclinical disease activity.
  - Anechoic area will be measured in the dermis before and after treatment, as well as other sonographic criteria of HS [10](See Appendix for Sonographic Scoring and Diagnosis of HS)
  - As there are no validated ultrasound criteria to measure clinical improvement, reduction in anechoic areas and sonographic criteria will be calculated. It is estimated that the treatment will induce a 50% reduction in the anechoic area.
  - Anechoic areas and other sonographic criteria will be correlated with PROMIS scores and Hurley Staging.
- Evaluation of cutaneous discharge
  - Swabs will be collected from discharge and sent for fluid count, which will include evaluation of infiltrating leukocytes from the discharge.
- Immunohistochemical Evaluation of HS Tissue Biopsies
  - Tissue biopsies will be collected before and after treatment. Tissue sections will be evaluated by H&E as well as immunohistochemistry for infiltrating leukocytes and other cells, such as T cells, B cells, plasma cells, dendritic cells, macrophages, and keratin. Image J will be used to quantify cells in a standard manner for comparison before and after treatment.

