#### 3.1 Inclusion Criteria

- The subject must be diagnosed with HS at Montefiore HS Treatment Center, with Hurley Stage 2-3 (Recurrent abscesses or boils with diffuse or broad involvement, multiple interconnected sinus tracts in the whole area) [5]. See Appendix A for photos.
- Subject must have failed maximal medical therapy for HS or be ineligible for "standard" medical therapy or surgery
- Age > 20 years old
- Women of childbearing potential must:
  - Have a negative serum or urine pregnancy test within 72 hours prior to the start of study therapy
  - Agree to utilize an adequate method of contraception throughout treatment and for at least 4 weeks after study therapy is completed. Adequate methods of contraception include hormonal methods (i.e. birth control pills, patches, injections, vaginal ring, or implants), barrier methods (i.e. condom or diaphragm), intrauterine device, or abstinence.
  - Be advised of the importance of avoiding pregnancy during trial participation and the potential risks of an unintentional pregnancy
- All patients must sign study specific informed consent prior to study entry.

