# Appendix B: Relevant Skin and Subcutaneous Tissue CTCAE Items[6]

Skin and Subcutaneous Tissue Disorders							
		G	Grade				
Adverse Event	1	2	3	4	5		
Bullous dermatitis	Asymptomatic; blisters covering	Blisters covering 10 - 30% BSA; painful blisters; limiting instrumental ADL	Blisters covering >30% BSA; limiting self care ADL	Blisters covering >30% BSA; associated with fluid or electrolyte abnormalities; ICU care or burn unit indicated	Death		
Dry Skin	Covering <10% BSA and no associated erythema or pruritus	Covering 10 - 30% BSA and associated with erythema or pruritus; limiting instrumental ADL	Covering >30% BSA and associated with pruritus; limiting self care ADL				
Pain of Skin	Mild pain	Moderate pain; limiting instrumental ADL	Severe pain, limiting self care				
Pruritus	Mild or localized; topical intervention indicated	Intense or widespread; intermittent; skin changes from scratching (e.g., edema, papulation, excoriations, lichenification, oozing/crusts); oral intervention indicated; limiting instrumental ADL	Intense or widespread; constant; limiting self care ADL or sleep; oral corticosteroid or immunosuppre ssive therapy indicated				
Skin hyperpigme ntation	Hyperpigmentation covering <10% BSA, no psychosocial impact	Hyperpigmentati on covering >10% BSA; associated psychosocial	-				

		impact			
Skin hypopigme ntation	Hypopigmentation or depigmentation covering <10% BSA; no psychosocial impact	Hypopigmentation or depigmentation covering >10% BSA; associated psychosocial impact			
Skin induration	Mild induration, able to move skin parallel to plane (sliding) and perpendicular to skin (pinching up)	Moderate induration, able to slide skin, unable to pinch skin; limiting instrumental ADL	Severe induration, unable to slide or pinch skin; limiting joint movement or orifice (e.g., mouth, anus); limiting self care ADL	Generalized; associated with signs or symptoms of impaired breathing or feeding	Death
Skin ulceration	Combined area of ulcers <1 cm; nonblanchable erythema of intact skin with associated warmth or edema	Combined area of ulcers 1 - 2 cm; partial thickness skin loss involving skin or subcutaneous fat	Combined area of ulcers >2 cm; full-thickness skin loss involving damage to or necrosis of subcutaneous tissue that may extend down to fascia	Any size ulcer with extensive destruction, tissue necrosis, or damage to muscle, bone, or supporting structures with or without full thickness skin loss	

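### The Grade 3 or higher safety event is defined differently across sections and never against the pre-treatment grade, so disease events could be counted, or true toxicity excused, by attribution alone

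*Combined protocol and SAP*

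**What the plan says.** The primary endpoint in Section 4.3 is safety, "defined as the absence of any treatment-related Grade" 3 or higher adverse event. The events counted are "treatment-related Grade ≥3 adverse events during radiotherapy or within 3 months of radiotherapy completion", scored on CTCAE version 4.0. Section 5.0 uses the treatment-related qualifier for its Grade 3 or higher interim rule (stop if more than 1 of 6) and for the final rule (accept if no more than 3 of 20, with no treatment-related Grade 4). Its interim Grade 4 clause has no qualifier.

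Section 4.1 is worded differently. Its general design paragraph stops the study for any toxicity above Grade 3, whatever the cause. Its Interim Analysis paragraph terminates the trial if "grade 3 or more toxicity is observed in more than 2 patients", or on any Grade 4 toxicity, again without the qualifier and with a different count from Section 5.0.

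The calendar in Section 4.2 schedules "Adverse Event Assessment" before treatment and at Weeks 1, 5, 9 and 13. No section says how the pre-treatment grade enters the endpoint. Section 9.1 defers the definition of an adverse event to an institutional policy that is not reproduced.

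Appendix B grades its terms by absolute severity. Grade 3 pain of skin is "Severe pain, limiting self care", and Grade 3 ulceration begins "Combined area of ulcers >2 cm; full-thickness skin loss" with subcutaneous damage. Section 3.1 enrols Hurley Stage 2-3 disease, described as "Recurrent abscesses or boils with diffuse or broad involvement" with interconnected sinus tracts, and excludes nobody for a Grade 3 skin finding at entry.

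**The concern.** Section 2.1 describes the disease as painful, with recurring abscesses, so skin pain is both a listed toxicity and a symptom that patients bring with them. Disease activity inside the 3-month window is also to be expected. The case report in Section 2.3 records recurrent lesions at 3 weeks and at 3 months after initial radiotherapy, and a new focus at 3 months. Section 4.4.2 directs treatment to one region, generally the most bothersome.

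In a single-arm trial, the boundary between a flare and a toxicity is an unblinded judgement, and the protocol gives no criteria for it. Under the Section 4.1 wording, even that judgement is not required. The error can go either way: a flare counted as toxicity pushes towards stopping or rejection, and a true toxicity put down to disease pushes towards acceptance. The cut-offs are small, so one or two such events can change the interim or the final decision.

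**Working it through.** **Inputs.** From Section 5.0: 6 patients in stage 1, stop at 2 or more events; 20 in total, reject at 4 or more; acceptable rate 10%, unacceptable rate 30%; stated probability of acceptance 80% and at most 10% respectively. The separate Grade 4 rule is left out because no Grade 4 rate is given.

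**Formula.** For an observed event rate p,

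P(accept) = Σ over x = 0, 1 of P(Bin(6, p) = x) × P(Bin(14, p) ≤ 3 − x).

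**Reproducing the plan's figures.**

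- p = 0.10: 0.5314 × 0.9559 + 0.3543 × 0.8416 = 0.5080 + 0.2982 = 0.806.
- p = 0.30: 0.1176 × 0.3552 + 0.3025 × 0.1608 = 0.0418 + 0.0486 = 0.090.

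Both agree with Section 5.0, so the design arithmetic is not in question.

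**Disease events counted as toxicity.** Let t be the true toxicity rate and b the assumed share of patients with a disease event wrongly counted, independent of toxicity. Then p = 1 − (1 − t)(1 − b). For example, t = 10% and b = 5% give 1 − 0.90 × 0.95 = 14.5%. The interim stop probability is 1 − (1 − p)^6 − 6p(1 − p)^5.

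| b (assumed) | p at t = 10% | P(stop at 6) | P(accept) | p at t = 2% | P(accept) |
|---|---|---|---|---|---|
| 0 | 10.0% | 11.4% | 80.6% | 2.0% | 99.4% |
| 2% | 11.8% | 15.1% | 72.9% | 3.96% | 97.4% |
| 5% | 14.5% | 21.2% | 60.4% | 6.9% | 91.3% |
| 10% | 19.0% | 32.0% | 40.0% | 11.8% | 72.9% |

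The 2% true rate is also an assumption. It is shown because 10% is the edge of the acceptable range.

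**True events excused as disease.** Let m be the assumed share of true events excused at a true rate of 30%, so p = 0.30 × (1 − m).

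- m = 0: p = 30%, P(accept) 9.0%.
- m = 10%: p = 27%, P(accept) 14.5%.
- m = 20%: p = 24%, P(accept) 22.1%.

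The last two exceed the stated 10% maximum.

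**The other interim cut-off.** The Interim Analysis paragraph stops only at 3 or more of 6. At t = 10% and b = 0, 2%, 5% and 10%, its stop probability is 1.6%, 2.5%, 4.3% and 8.7%. With that cut-off and the same final rule, P(accept) is 86.4% at 10% and 10.6% at 30%, so the stated 10% limit is narrowly missed. The two sections therefore differ both in what they count and in how many events stop the trial.

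**The case against.** The strongest reply is that the treatment-related qualifier in Sections 4.3 and 5.0 already excludes disease events when correctly applied. Investigators will have a pre-treatment assessment, an examination and photographs to help them. The institutional policy cited in Section 9.1 may require an event to be new or worsened. Section 8.0 has a monitoring committee review Grade 3 or higher events, and the DSMB must approve stage 2. The missing qualifier in Section 4.1 may be shorthand, and the interim cut-off there is the less sensitive one. Section 2.3 reports no acute side effects among 231 treated patients, and Section 10.0 calls the dermatitis risk very low, so true toxicity may lie well below 10% and leave more room.

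Much of this stands. A reader might infer that disease events will be counted as toxicity; the documents support only that they can be. A reader might also infer that ulceration is a documented feature of the disease. Sections 2.1 and 3.1 name abscesses, sinus tracts and, in Section 2.1, scarring, but not ulceration, and the Grade 3 ulcer threshold also requires full-thickness loss. Skin pain is the supported example. Nor does two of six stop the trial under every section.

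The reply does not dispose of the inconsistency. The same interim look is written on two different events with two different counts, and committee review does not supply a criterion for telling a flare from a toxicity.

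**Conclusion.** The point holds as a defect in the definition of the primary safety event: it is inconsistent across sections, not referenced to baseline, and dependent on unblinded attribution without stated criteria. It is not a finding that the trial's result will be wrong.

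The size cannot be fixed from the documents. At 10% true toxicity, a 2% miscount costs about 8 points of acceptance probability (80.6% to 72.9%) and a 10% miscount about 41 points (80.6% to 40.0%). At 2% true toxicity, only the 10% miscount has a large effect. Excusing even 10% of true events at a 30% rate breaks the stated 10% limit. These figures assume the Section 5.0 rule, independence of disease events and toxicity, and no Grade 4 events.

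It would also be too strong to infer that a baseline rule restores the stated operating characteristics. A new flare after treatment is still new, and so still needs attribution. The rule also does not prevent a true event from being excused.

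**What to change.** - Use one event definition in Section 4.1 (both paragraphs), Section 4.3 and Section 5.0: a treatment-related adverse event that reaches Grade 3 or higher and is new or worse than the same CTCAE term at the pre-treatment assessment. State how relatedness is judged when the event resembles the disease.
- Reconcile the interim cut-offs in Section 4.1 (more than 2) and Section 5.0 (more than 1), and the Grade 4 clauses, which carry the qualifier in some places and not in others. Check that the stated operating characteristics match the rule that is kept.
- List separately any patient already at Grade 3 on a term at baseline. Appendix B gives no Grade 4 for pain of skin, so such a patient could otherwise never count on that term, which would push towards acceptance.
- Report all-cause Grade 3 or higher events, with exact 95% intervals, beside the primary result. Section 5.0 already plans such intervals for treatment-related toxicity. The gap between the two rates shows how much the conclusion owes to attribution, in either direction.

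The cost is a protocol amendment to wording and one extra summary table. The pre-treatment assessment is already scheduled, so no visit or measurement is added.
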